## 1. Introduction

With an increasing global prevalence of knee OA (KOA) and no highly effective treatments for pain, there is an urgent need to improve conservative pain management strategies to avoid the associated negative outcomes such as limited mobility and multimorbidity [1]. Current clinical practice guidelines strongly recommend exercise and patient education as the core conservative management strategies [2,3]. Various types of exercises are recommended including neuromuscular exercises which are focused on improving knee functionality [4]. However, these treatments are only moderately effective for controlling pain [5], which therefore begs for a deeper understanding of the mechanisms of KOA pain and filling the corresponding gaps with mechanism-based treatment strategies.

Current recommended methods for conservative management are not predicated on pain mechanisms, while evidence for neural sensitization and dysregulation of intrinsic pain modulation is widely reported [6]. Mind-body approaches have the potential to fill these gaps in the management of KOA through a combination of physical postures, breathing techniques, meditation, mindfulness, and relaxation [7]. The effects are reported to be mechanistically related to the regulation of nociceptive signals [8]. For instance, breathing exercises can lead to the disruption of the association of pain and sympathetic nervous system activation [9], leading to modulation of autonomic functions [10]. Meditation and relaxation can create a state of calm and provide a sensation of being in a place of safety (a parasympathetic state) [11], which can lead to changes in one's pain experience [12]. Mindfulness and mindful movements can improve where and how to focus, develop skills to control the response to pain [13], and influence the pain experience through emotional regulation and interoception [8].

A management strategy that can be a valuable addition to exercise,

Pain Neuroscience Education (PNE) is a technique that shifts the focus from the diseased knee joint and the assumption that pain stems from degenerative structural changes [14]. Unlike standard OA education that has historically had a biomedical influence [14], PNE reconceptualizes pain as a danger signal and introduces intrinsic modulation of pain to influence the pain experience. Omitting biomedical language from KOA education can lead to significantly lower perceptions that physical activity is injurious to the knee joint, lower fear of movement, and improve participation in exercise [14]. Combined with active treatment strategies such as exercise, PNE results in positive changes in pain [15].

The need for high quality research that evaluates the effects of mind- body approaches in managing KOA pain and understanding how they may modify altered nervous system processing is needed. Our group has developed a program we call Pain Informed

Movement, which is a combination of neuromuscular exercise, mind-body techniques, and PNE with the aim of improving intrinsic pain modulation in people with KOA. Although each of these components as a standalone technique can improve pain in KOA, their cumulative effect may be more substantial and has the potential to lead to an enhancement of outcomes, as each component can lead to optimization of the other. Given that the feasibility and acceptability of the Pain Informed Movement program has been previously established [16], further evaluation of this program compared to standard care is warranted. This paper presents a detailed protocol for a pilot randomized controlled trial (RCT) to collect pilot data, as well as initial efficacy data on the comparison of Pain Informed Movement program with neuromuscular exercise and standard OA education in people with KOA. This study has been approved by the Hamilton Integrated Research Ethics Board and registered on clinicaltrials.gov (ID: NCT05730829).

### **1.1. Study objectives and hypothesis**

The objectives of this study are 1) to pilot test the procedures of this RCT and investigate the feasibility with the primary outcome of rate of follow-up, 2) assess secondary aspects of feasibility such as acceptability of the programs, rates of recruitment, adherence, compliance, as well as burden and adverse events) and 3) explore effects of Pain Informed Movement program on subjective and objective measures of KOA pain when compared to a usual conservative management strategy for people with KOA. Given the additional and improved components of the Pain Informed Movement program and its feasibility established in the previous phase [16], we hypothesize that this pilot RCT will show feasibility of comparing the two treatment strategies, and the Pain Informed Movement program will show promising results.

## **2. Methods**

### **2.1. Study design**

This is a pilot study with a nested qualitative component designed as a parallel, randomized, single-centre, two-arm clinical trial with a 1:1 allocation ratio. Informed consent will be obtained from all participants prior to initiating the study. All participants will be invited to complete an exit survey and take part in focus group interviews at program completion. Fig. 1 depicts the trial design. The procedures will be followed in accordance with the ethical standards of the responsible committee on human experimentation (institutional and national) and with the Helsinki Declaration of 1975, as revised in 2000. The Conceptual Framework for Defining Feasibility [17] and Pilot studies and the Standard Protocol Items: Recommendations for Intervention Trials will be used [18]. Following

program completion, the study results will be reported using the extended CONSORT guideline for pilot trials as well as the TiDIER guidelines [17,19]. The study protocol is registered at [clinic trials.gov #NCT05730829](https://clinicaltrials.gov/ct2/show/NCT05730829).

## **2.2. Study participants**

Sample size is based on the primary outcome of complete follow-up using the confidence interval method for calculating sample size in pilot trials [20]. We will aim for 90% follow-up but will consider the trial successful if we achieve 81%. To achieve a margin of error of 9%, with 10% added for attrition, we will require 66 participants (n ¼ 33 per arm).

Participants will be recruited through the email lists of the McMaster University's community and research centers and their social media pages. Additionally, the study poster will be placed on other social media channels (e.g., Twitter, Facebook advertisements) and flyers will be placed in local Orthopaedic surgeon, Rheumatologist, and Psychiatrists offices.

The inclusion and exclusion criteria are listed in Table 1.

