### **2.7. Primary and feasibility outcomes**

The primary outcome measure is the follow-up rate (i.e., number of participants that completed the program and attended follow-up). Other feasibility outcomes include: acceptability (content, format, frequency, and duration) of the Pain Informed Movement program compared to the control group, recruitment rate, burden of procedures, adherence rate (i.e., number of participants that attended all in-person sessions), compliance to the program (i.e., number of participants that reported completion of at least three exercise sessions per week), and AEs. A priori success criteria will be used to determine feasibility and acceptability of the programs (Table 2).

Table 2:

*A priori* feasibility criteria.

Outcome	A priori criteria		
	Proceed	Proceed with protocol amendments	Significant amendments required
Follow up	≥90% of participants followed up at 8 weeks	≥50% of participants followed up at 8 weeks	≤50% of participants followed up at 8 weeks
Recruitment	≥40 participants consent to participate/year	≥30 participants consent to participate/year	<30 participants consent to participate/year
Compliance to exercise program	≥80% of participants report exercise at least 3 times a week	≥50% of participants report exercise at least 3 times a week	<50% of participants report exercise at least 3 times a week
Program content acceptability – usefulness	≥50% found treatment useful (Likert ≥4/5)	≥25% found treatment useful (Likert ≥4/5)	<25% found treatment useful (Likert ≥4/5)
Program content acceptability – frequency	≥50% found frequency acceptable (Likert ≥4/5)	≥25% found frequency acceptable (Likert ≥4/5)	<25% found frequency acceptable (Likert ≥4/5)
Program content acceptability – duration	≥50% found duration acceptable (Likert ≥4/5)	≥25% found duration acceptable (Likert ≥4/5)	<25% found duration acceptable (Likert ≥4/5)
Format acceptability – delivery	≥50% found treatment delivery (in-person and home) acceptable (Likert ≥4/5)	≥25% found treatment delivery acceptable (Likert ≥4/5)	<25% found treatment delivery acceptable (Likert ≥4/5)
Adherence to in person treatment	≥75% of participants attended all in person treatment sessions	≥50% of participants attended all in person treatment sessions	≤25% of participants attended all in person treatment sessions

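### Two different bars for the primary outcome: section 2.2 counts 81% follow-up as success, while Table 2 gives an unqualified go-ahead only from 90%

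*Combined protocol and SAP*

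**What the plan says.** Section 1.1 names the rate of follow-up as the primary outcome. Three places then bear on what counts as enough.

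- Section 2.2, in the sample size paragraph: "We will aim for 90% follow-up but will consider the trial successful if we achieve 81"%. The next sentence gives a 9% margin of error and, "with 10% added for attrition, we will require 66 participants".
- Section 2.7, text: the outcome is the "number of participants that completed the program and attended follow-up", and "A priori success criteria will be used to determine feasibility and acceptability of the programs (Table 2").
- Table 2, follow-up row: *Proceed* at "≥90% of participants followed up at 8 weeks"; *Proceed with protocol amendments* at "≥50% of participants followed up at 8 weeks"; *Significant amendments required* at "≤50% of participants followed up at 8 weeks".

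Section 2.11 plans descriptive statistics only for the feasibility outcomes. The figure of 81% does not appear in Table 2, and no text relates success in section 2.2 to a Table 2 tier.

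**The concern.** Either bar would be acceptable alone. The difficulty is that both are set in advance for the same outcome and they differ by nine percentage points. As no hypothesis test is planned for follow-up, the threshold is the only decision rule the primary outcome has. A result in the 80s could be reported as plain success by citing section 2.2, or as a need for amendments by citing Table 2, and the choice could be made after the data are seen. Criteria fixed in advance are meant to prevent that.

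**Working it through.** **Inputs.** Success bar 81%, aim 90%, margin 9%, attrition 10% and N = 66 (section 2.2); tier bars 90% and 50% (Table 2). Assumptions: the denominator is all 66 randomised; the confidence level is 95%; participants are followed up independently with a common probability p.

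**The plan's own figure.** The usual formula for a single proportion is n = z²p(1−p)/d². With p = 0.90, d = 0.09 and z = 1.96 it gives 42.7, so 43. Allowing for 10% attrition gives 48 (43/0.9 = 47.8, or 43 × 1.1 = 47.3). The stated 66 is not reproduced, so the calculation does not show what 81% was meant to be. The total comes close to 66 only with inputs the plan does not state, such as p = 0.855 at 95% confidence (59, then 65 or 66) or 98% confidence at p = 0.90 (61, then 68). The point below does not depend on this.

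**Counts.**
- 81% bar: 0.81 × 66 = 53.46, so at least 54 (54/66 = 81.8%; 53/66 = 80.3%), at most 12 lost.
- 90% bar: 0.90 × 66 = 59.4, so at least 60 (60/66 = 90.9%; 59/66 = 89.4%), at most 6 lost.
- In conflict: 54 to 59 followed up, that is 7 to 12 lost.

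The attrition allowance sits at the edge of this range. It is 6.6 people as 10% of 66, or 6 if 66 was formed as 60 × 1.1. Six lost is *Proceed* in both places; with seven lost the two sections disagree.

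**How likely the conflict is.** With X ~ Binomial(66, p):

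| True rate p | P(54 ≤ X ≤ 59), in conflict | P(X ≥ 54), meets 81% | P(X ≥ 60), meets 90% |
|---|---|---|---|
| 0.78 | 0.28 | 0.28 | 0.01 |
| 0.80 | 0.41 | 0.43 | 0.01 |
| 0.85 | 0.70 | 0.82 | 0.12 |
| 0.88 | 0.64 | 0.95 | 0.31 |
| 0.90 | 0.48 | 0.99 | 0.51 |
| 0.92 | 0.27 | 1.00 | 0.73 |
| 0.95 | 0.05 | 1.00 | 0.95 |

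**The alternative reading of 81%.** Since 90 − 9 = 81, the figure may have been intended as a lower confidence limit. Lower limits of the two-sided 95% interval with N = 66:

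| Followed up | Wald | Wilson | Clopper-Pearson |
|---|---|---|---|
| 54 | 72.5% | 70.9% | 70.4% |
| 58 | 80.0% | 77.9% | 77.5% |
| 59 | 82.0% | 79.7% | 79.4% |
| 60 | 84.0% | 81.6% | 81.3% |

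A lower limit of at least 81% therefore needs 59 (Wald) or 60 (Wilson, Clopper-Pearson), against 54 for an observed rate. The two meanings of 81% differ by five or six participants.

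**A smaller point in the same row.** 33/66 is exactly 50% and meets both the middle and the lowest tier. The compliance row avoids this with "<50% of participants report exercise at least 3 times a week".

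**The case against.** The strongest reply is the confidence-limit reading. The 81% stands in a paragraph about a confidence interval method, directly before the 9% margin, and on that reading the section 2.2 bar is 59 or 60 of 66, within one participant of Table 2. This is plausible, and it means that the 54 to 59 range and its probabilities hold only if 81% is an observed rate. But the sentence speaks of achieving 81%, which reads as an observed rate; no passage calls it a limit; and section 2.11 does not plan an interval for follow-up. The sponsor still has to say which is meant.

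A second reply is that calling a trial successful and grading the next step are different things, so a pilot at 85% could be successful and still lead to amendments. That is why the conflict is no worse than unqualified success against a conditional go. It does not reconcile the two bars: the amendments tier starts at 50%, so 81% matches no boundary in Table 2, and a rate from 50% to below 81% would then be a form of proceeding without being a success.

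A third reply is that the two places may not count the same event. Section 2.2 speaks of complete follow-up, the section 2.7 text requires both program completion and attendance, and Table 2 refers only to follow-up at 8 weeks. This stands, and is a further reason to use one wording.

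**Conclusion.** The concern holds. The plan gives two unreconciled thresholds, 81% and 90%, for its primary outcome. On the observed-rate reading, with all 66 as the denominator, results of 54 to 59 followed up (81.8% to 89.4%) receive different labels. The probability of such a result is 48% at the plan's own target of 90%, between 64% and 70% at true rates of 88% and 85%, and 5% at 95%. On the confidence-limit reading, at most one count (59, with the Wald interval) remains in the gap, but that reading is not written down. That the two passages are unreconciled is certain; the size of the conflict depends on the reading and the denominator. It should be fixed, but it does not threaten the trial.

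**What to change.** Before results are known, state one follow-up criterion in identical words in section 2.2 and Table 2. Name the event counted, take all randomised participants as the denominator, and report the rate with a 95% confidence interval by a method named in advance.

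- **Default:** keep Table 2's 90% bar (60 of 66) for *Proceed*, because section 2.7 makes Table 2 decisive. Delete the 81% success statement, or have the sponsor state what it represents, for example a lower confidence limit. If it is deleted, keep a stated rationale for the 9% margin, since 90 minus 9 is the only visible link between the two figures.
- **If 81% is intended as an observed-rate bar:** change the Table 2 row to *Proceed* from 81% and amendments from 50% to below 81%, and state that a true rate of 80% would then earn *Proceed* about 43% of the time, and a true 78% about 28%.
- **Tidy-up:** make the lowest follow-up tier below 50%, so that 33 of 66 falls in one tier.

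The edit is one sentence and one table row, with no new data or participants. The price of the default is that a true 90% rate earns an unqualified *Proceed* only about 51% of the time (95% at a true 95%); otherwise the result falls almost always in the amendments tier.

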**Table 1**  
Inclusion and exclusion criteria.

Inclusion criteria	Exclusion criteria

≥40 years of age with diagnosis of knee osteoarthritis (KOA by) a physician
 
OR ≥45 years of age and having
 
activity-related knee joint pain with or without morning stiffness lasting ≤30 min (NICE criteria)
 
2 Having an average pain intensity of at least 3/10 on a numeric pain scale on most days of the past month
	
1 Cannot communicate in English
 
3 Has inflammatory arthritis or other systemic conditions
 
4 Has had lower limb trauma or surgery within the past 6 months
 
5 Has participated in a KOA exercise program in the past 3 months
 
1 Has had any injection in the index knee within 3-months prior to baseline assessment
 
2 Does not have regular access to the internet
 
3 Inability to get up and down from the floor independently
 
4 Use of mobility aids
 
5 Currently participating in any other drug/device/exercise clinical trial related to OA
 
6 Planned absences (e.g., trips away) of >1 week
 
7 Currently receiving other forms of care for KOA pain (e.g., from a physiotherapist, chiropractor, athletic therapist, kinesiologist)
 
8 Does not meet screening for safe participation in exercise according to the Get Active questionnaire from the Canadian Society for Exercise Physiology [25]

[figure not shown]
### 2.3. Screening and assessments

Potential participants will contact the research team through the contact information provided in the flyer and study poster. Screening will be conducted over the telephone and study information will be provided. Consenting and eligible participants will be sent an individualized link to the written consent form, written study information, and baseline

questionnaires. Those who pass the screening, including exercise safety, will be invited to an in-person physical assessment. Upon program completion, participants will be sent the questionnaires again (which also include the exit survey questions) and will attend a second in-person assessment of physical measures. Focus groups will be conducted to further assess the participants' perception of the study. If a participant has bilateral KOA, the most symptomatic knee will be studied. If both knees are equally affected, the dominant knee will be studied, which is the knee with which the individual steps first when initiating gait.

#### **2.4. Randomization and blinding**

Participants will be randomized with an allocation ratio of 1:1 into one of two treatment groups (Pain Informed Movement or neuromuscular exercise and standard OA education) using a REDCap randomization module. The process of randomization will be conducted by a member of the research team who is independent of the recruitment process. Additionally, the assessors responsible for conducting baseline and follow-up assessments will be blinded and not involved in recruitment. Blinding of exercise instructors is generally not possible in studies of physical interventions (e.g., exercise) [21]. Participants will be blinded to study hypotheses and the two treatment groups. As both arms of the study are providing exercise-based interventions and education, participants will be provided limited details of each intervention arm so as to blind them from knowing which is the intervention and which is the control. This will help minimize any bias that occurs by knowledge of group assignment and perception of treatment effects.

## 2.5. Interventions

The intervention will start within two days of the physical assessments with participants receiving educational videos approximately 10–14 days before the first exercise session.

### 2.5.1. Pain Informed Movement program

Participants in this group will receive an 8 week in-person group exercise program held twice weekly, in which they will receive exercise instructions and PNE. They will also be

asked to complete a third exercise session at home weekly. Participants will be provided with tracking sheets to note their compliance and progress.

The PNE component will consist of several short videos that are provided online for the first five weeks of the program (the videos are divided into short segments, each with a separate subject, totaling 20–30 min/week)). The videos will provide simple explanations of nociception processing by the nervous system, how it can be modulated through upregulation or downregulation of signals to increase or decrease pain and that pain does not accurately signify the extent of tissue damage, particularly when experiencing chronic pain. The videos will also offer techniques to reconceptualize pain and movement not as imminently dangerous. In addition, the videos will introduce and provide a demonstration of mind-body techniques that will be provided progressively each week. The mind-body techniques will include breath awareness and regulation, body awareness and muscle tension regulation, and awareness of pain related thoughts and emotions. The techniques will then be implemented in the in-person exercise sessions where participants are asked to incorporate them into their performance of the exercises. Instructions will be provided on how to ‘nudge the edge’ of pain which is conceptualized as a balance between challenging current physical abilities during the exercises and being successful at not leaving pain provoked and/or function limited after exercise. Participants will be instructed to use breath, body tension, thoughts, and emotions as guideposts to their pain in order to successfully nudge its edge. Participants will be given the opportunity to ask questions during the in-person sessions.

The exercise component (75 min) will consist of three parts (in sequence):

Part one: the first part is the warm-up which begins with a centering practice aimed at regulating physiology. Next, warming movements of the shoulders, legs, and spine will be instructed.

Part two: of the second part is the main exercises (based on the original NEMEX-training program [4]) This part is divided into four sections: core stability, postural orientation, lower extremity muscle strength, and functional exercises with an emphasis on proper alignment of the knee over the foot. Within each section, there are two types of exercises and three levels for progression. Participants will be instructed to complete each exercise for two to three sets of eight to 15 repetitions. For the core stability section, one exercise is instructed based on breaths. When an exercise is performed with good quality of the performance, with minimal exertion, and with control of the movement, it can be progressed by increasing repetitions or the load (going through the levels). The exercises will be performed with both the affected and the unaffected leg.

Part three: the third and last part is cooldown which consists of the same warmup movements plus relaxation and guided self-reflection. Participants will be cued to use the PNE concepts and mind-body techniques during the exercise sessions.

Participants will also complete a third home session (weekly) which is facilitated by handout sheets. The exercise component will be delivered by an experienced yoga teacher with training in the integration of pain science and mindful movement.

### **2.5.2. Neuromuscular exercise and standard OA education**

Participants in this group will receive an 8-week in-person group exercise program held twice weekly, in which they will receive exercise instructions and standard OA education. Participants will be provided with tracking sheets to note their compliance and progress.

The exercise component (60 min) of this group will be similar to that of the other group without the added mind-body techniques. Similarly, a third home session (weekly) will be facilitated by exercise handout sheets. The exercise instructions will be delivered by a physiotherapist. The standard OA education will consist of several short videos (20–30 min/week for the first two weeks provided through online videos) and will cover the following topics: pathophysiology of OA, common OA symptoms, risk factors, the effects of exercise, and self- management tips. Participants will be given the opportunity to ask questions during the in-person sessions.

